7.0 STUDY CRITERIA

Observations and Tests

The following observations and tests are to be performed and, where appropriate, recorded on the designated form(s) (Appendix A):

PARAMETER	Pre-operative	Intraoperative	Postoperative
Log on approached patient	X		
Log on included patients and patients' withdrawal from study before surgery	X		
History & Physical examination Examination and evaluation by surgeon and anesthetist	X		
Measurement of leg volume	X		X
Lymphedema Quality of Life questionnaire	X		X
Lymphedema symptoms score			X

Laboratory test Hb, S-electrolytes, S-kreatinine CRP, Trc, coagulation test when appropriate	X		X
Injection data for ICG including drug related adverse events	X	X	X
Sentinel nodes identification		X	
Recording of intraoperative adverse events		X	
Histologic evaluation of sentinel nodes and non-sentinel nodes			X
Recording of post-op complications until 30 days after surgery (Claviden Dindo)			X

Adverse Events will be captured from time of ICG administration until 30 days after surgery. See section 10.

8.0 EVALUATION CRITERIA

- All patients who are injected with ICG with at least one SLN type1-2, macro and SLN anatomy and not converted to open surgery before detection and removal of SLN's will be included for evaluation of detection rate of metastatic pelvic nodes all together and with evaluation of ICG defined (SLN type1-2) separately.
- Time used for the study intervention (Injection and reinjection of ICG and detection / removal of SLN's) shall be separately recorded
- All patients included, regardless of conversion to open surgery and mapping of ICG will be included in the overall evaluation of feasibility and safety.
- Intraoperative adverse associated with the detection and removal of SLN will be evaluated and reported separately on all patients who have at least one SLN removed regardless of type, i.e all patients in whom SLN were removed separately.
- Postoperative complications until 30 days after surgery will be reported.

-Perioperative and postoperative complications related restaging will be evaluated on an intention to treat basis.

-An increase in leg volume of 10 % or more compared with the preoperative volume will be defined as a new onset of lymphedema.

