1. OBJECTIVES

To estimate the efficacy of a pelvic sentinel lymph node (SLN) concept for diagnose of pelvic nodal metastases in patients with low and- high risk endometrial cancer using a cervical injection of Indocyanine Green (ICG) as tracer and robot assisted near infrared (NIR) imaging using an anatomically based surgical algorithm and definition of sentinel lymph nodes. The observed percentage of metastatic sentinel nodes will be evaluated from a non-inferiority perspective based on an assumed percentage of pelvic nodal metastases estimated from final detailed histological data (myometrial invasion, cervical stromal invasion, histological type and grade)

To estimate the proportion of low- and high risk endometrial cancer patients suitable for the SLN concept in conjunction with robotic surgery

To estimate time for the SLN procedure and intraoperative complications associated with detection of SLN as such (study intervention) and postoperative adverse events until 30 days as well as objective measurement of leg volume and lymphedema symptoms by the use of a validated questionnaire up and until two years after surgery.

To estimate health economy aspects of the SLN concept.

To estimate complications associated with ICG as tracer

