The ICG solution is prepared immediately before surgery and intended for single patient use. For preparation, 10mL of sterile water is injected directly into the lyophilized ICG in its glass vial. Invert the vial multiple times to ensure thorough mixing. Draw up 0,25 mL in six 1 mL syringes from the vial with ICG solution (2,5mg/mL) for the cervical injection. A 0.6x38mm 23Gx1 1/2 needle. The content of four of the syringes are used for the initial injection and in case of non-display of any pathway one or two of the other are used for an ipsilateral re-injection.

The ICG solution is stored at room temperature. The solution is active for 6 hours, and should be discarded after that period of time.

Manufacturer: Pulsion medical system, Feldkirchen Germany

Availability: ICG will be provided by the manufacturer to each site.

Adverse Effects if ICG: All adverse effects are allergic in nature and occur in <1% of patients. Anaphylactic or urticarial reactions have been reported in patients with or without a history of allergy to iodides. If such reactions occur, treatment with the appropriate agents (e.g. adrenalin, antihistamines, corticosteroids) should be initiated.

Contraindications: Known hypersensitivity to iodine containing compounds. Known liver failure. Radioactive iodine uptake studies should not be performed for at least 1 week following the use of ICG.

Please refer to the current ICG package insert for complete prescribing information

Injection of Indocyanine Green (ICG)

- The ICG is prepared by thorough mixing of 10mL of sterile water with the lyophilized ICG in its vial creating a 2.5mg/mL concentration. The lot number, expiration date and dose injected (mg) will be recorded.
- Six separate sterile 1mL syringes is prepared with 0.25 mL ICG solution (0.625 mg ICG) in each syringe is prepared.
- A 0.6x38 mm 23G needle is attached to each syringe for the injection. A separate back table is used for the syringes.
- The ICG injection will be performed immediately before placement of surgical port and docking the robot.
- Half the ICG volume in each syringe is injected submucosally and half the volume 3 cm into the cervical stroma at 2-4-8-and 10 O'clock respectively to a total dose of 2.5mg ICG and a total volume of 1 mL. Time for injection is recorded.
- After injection of dye, a fornix presenter without an intracervical device is placed

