6.0 TREATMENT MODIFICATIONS

In case of conversion to open surgery before identification and removal of SLN's the patients should be included in evaluation of adverse events and feasibility on an intention to treat basis but not included in the calculation of sensitivity and negative predictive values for the sentinel node concept.

A pelvic lymphadenectomy shall be performed based on definition of "SLNmacro" and/or "SLN-anatomy". SLN macro shall be evaluated with frozen section and if positive a paraaortic lymphadenectomy shall be performed unless contraindicated.

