10 STUDY MONITORING AND REPORTING PROCEDURES

ADVERSE EVENT REPORTING

The study protocol has been revised related principles study monitoring and for reporting adverse events to the principal investigating center after inclusion of the second center.

Definitions

An adverse event (AE) is any new medical problem or exacerbation of an existing problem experienced by a subject enrolled in the study, whether or not it is considered drug-related by the investigator.

This study will utilize the Adverse Events Logs (Tables 10.1-5). Any SAE will be reported to the study coordinator ([contact]) using the SAE log. (appendix 1).

Adverse events related to the study drug (ICG).

All adverse events occurring from the first dose of study drug until hospital discharge (whether or not attributed to the study drug) will be reported on the Adverse Event Log. In addition, any adverse event reported by the subject to the investigator after discharge and determined to be reasonably associated with the study drug should also be captured and followed until resolution.

Adverse events related to the sentinel node procedure as such (excluding AE related the study drug, ICG)

All intraoperative events related to the SLN procedure will be reported on the adverse events log.

Adverse events related the surgical procedure (excluding the SLN part) including AE until 30 postoperative days.

All adverse events will be reported on the adverse events log.

Serious adverse event (SAE):

An adverse event that results in one or more of the following:

- Any death occurring prior to the postoperative outpatient evaluation 30 days postoperatively.
- Any life-threatening event until and including 30 postoperative days.
- Any medical event requiring inpatient hospitalization or prolongation of existing hospitalization beyond five postoperative days

NOTE: Hospitalizations that are not considered SAE are:

- Hospitalization planned prior to first administration of study drug
- Hospitalization for elective treatment of a pre-existing condition unrelated to the study medication
- Hospitalization due to social / practical reasons such as an untimely coordination with local community home care services.

Attribution: Attribution is the determination of whether an adverse event is related to a medical treatment or procedure. The categories of attribution are:

Definite: The adverse event is clearly related to the study drug

Probable: The adverse event is likely related to the study drug.

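### The separate SLN complication rate covers detection but counts only women with a node removed, so injuries that end the procedure before any removal are left out of that rate

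*Combined protocol and SAP*

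**What the plan says.** Section 8 defines the events and the women for this report in one bullet. The events are those "associated with the detection and removal of SLN will be evaluated and reported separately". The women are restricted: the events are "reported separately on all patients who have at least one SLN removed regardless of type, i.e all patients in whom SLN were removed separately".

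Other sections bear on the same estimate:

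- Section 1 sets out to estimate "intraoperative complications associated with detection of SLN as such (study intervention", with no condition that a node was removed. Complications of ICG as tracer are a separate objective.
- The preceding safety bullet of Section 8 is unrestricted: "All patients included, regardless of conversion to open surgery and mapping of ICG will be included in the overall evaluation of feasibility and safety".
- Section 6, on conversion to open surgery before SLNs are identified and removed, states that "the patients should be included in evaluation of adverse events and feasibility on an intention to treat basis".
- Section 10 requires that "All intraoperative events related to the SLN procedure will be reported on the adverse events log", and defines this category as excluding events related to ICG. Table 10.2 is a log for the sentinel node dissection phase.
- The surgical form (Appendix 2) has a complications field that is worded for SLN removal only.

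**The concern.** The event definition and the analysis set do not match. Detection is in scope for events, yet a woman enters the set only if the procedure went on to removal. Removal happens after exposure to detection and dissection has begun, and an injury during that exposure is one reason why removal may not happen. Inclusion in the denominator can therefore depend on the outcome being measured.

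The separate rate is what a reader would use to judge the harm of the SLN procedure itself. Section 11 presents the procedure as a replacement for full lymphadenectomy in high-risk women and as an added diagnostic procedure in low-risk women. The overall safety figure cannot take its place, because it also contains events from port placement, hysterectomy and lymphadenectomy.

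**Working it through.** **1. Exposure that precedes removal.** Under Sentinel Node Identification (Section 4.0/5.0), display of the upper pathway is assessed at least 10 minutes after injection, first through the peritoneum. If it is not seen, the retroperitoneal planes are opened, and reinjection follows if display still fails. An operative injury at this stage belongs to detection and can occur before any node is out.

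**2. Who has no SLN removed.** Failed mapping alone does not exclude a woman. Nodes at typical positions are then taken and count as SLN-anatomy, and macroscopically suspect nodes count as SLN macro. What remains is mainly women whose procedure was converted or stopped before any removal. The form's conversion causes are technical (robot), surgical and anaesthetic, so only some of these women would have an SLN injury.

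**3. Direction of the bias.** Let q be the share of women with no SLN removed, e0 the SLN-event rate among them, and e1 the rate among women with removal. Then

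rate(all) = (1 − q)·e1 + q·e0, so rate(all) − rate(removed only) = q·(e0 − e1).

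The removed-only rate is too low if e0 > e1, unchanged if they are equal, and slightly too high if e0 < e1.

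**4. Base number.** The plan states no SLN complication rate to reproduce. Its only relevant figure is N = 362 (Section 11). A two-stage exact binomial calculation (8% against 12%, first stage 150, stop at 12 or fewer or at 22 or more) with a final cut-off of 38 gives alpha 0.0497 and power 0.801, so 362 reproduces. The cut-off of 38 is assumed, because the plan does not state one. Here 362 serves only as the base for illustration.

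**5. Range under assumed values.** The documents give neither q, e0 nor e1. With e1 = 1%, the rate in all women is:

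| q (women of 362) | e0 = 0 | e0 = 50% | e0 = 100% |
|---|---|---|---|
| 1% (about 4) | 0.99% | 1.49% | 1.99% |
| 2% (about 7) | 0.98% | 1.98% | 2.98% |
| 5% (about 18) | 0.95% | 3.45% | 5.95% |

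The removed-only figure is 1% in every cell. Taking e1 as 1% or 2%, the difference (all minus removed only) runs from 0.05 × (0 − 0.02) = −0.10 to 0.05 × (1 − 0.01) = +4.95 percentage points.

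**6. The same in counts (assumed; exact 95% intervals).**

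- All women: 4/362 = 1.10% (0.30 to 2.80).
- Two of the four events end the procedure before any removal: 2/360 = 0.56% (0.07 to 1.99).
- All four do: 0/358, upper limit 1.03%.
- Opposite case, 18 women without events left out: 4/344 = 1.16%.

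With rare events, leaving out event-free women barely moves the rate, while losing even two events can halve it.

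**The case against.** The strongest reply is that nothing is lost. Sections 6 and 8 keep every included woman in overall safety, Section 10 logs SLN-procedure events without any removal condition, and serious ones go to the Safety Monitoring Committee. This stands. A reader might infer that events ending the procedure vanish from the trial, or that Sections 6 and 8 contradict each other on overall safety. The documents support neither. The gap is confined to the separate SLN rate.

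Three further points also stand, in whole or in part:

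- **ICG reactions.** It is tempting to count an allergic reaction that aborts surgery as an omitted event. Section 10 excludes drug-related events from the SLN-procedure category, and Section 1 gives them their own objective. The broader description of the intervention in Section 8, which includes injection, belongs to the bullet on time recording.
- **Certainty of direction.** A reader might infer that the rate can only err towards safety. Women converted for unrelated causes before SLN work began have no SLN event, and leaving them out raises the rate slightly.
- **Size of the group.** One node of any type on either side is enough to enter the set, and in high-risk women removal starts presacrally. Directly after its conversion rule, Section 6 calls for a pelvic lymphadenectomy based on the SLN-macro and SLN-anatomy definitions. If this applies to converted women, some stay in the set.

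These points limit the size of the problem. They do not remove the mismatch between a detection outcome and a set defined by removal.

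**Conclusion.** The concern holds in limited form. The SLN-specific intraoperative rate is conditioned on a post-exposure event that the complication can itself prevent, and it does not cover the full scope of the objective it serves. It is likely, though not certain, to be biased low. Under the assumed ranges the rate in all women differs from the removed-only rate by −0.10 to +4.95 percentage points. The upper end needs 5% of women without any SLN removed and an SLN injury in every one of them, which nothing in the documents suggests. The rate is descriptive, with no test or stopping boundary attached, and the primary test and N = 362 are unaffected. The correction is still worth making because it is cheap and the rate informs the safety argument for the SLN concept.

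**What to change.** In Section 8, change the set for SLN-associated intraoperative adverse events as follows:

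- **Main rate:** all women in whom SLN detection or dissection was started, regardless of conversion and of whether any SLN was removed. Define the start point, for example the first inspection for ICG display after docking, and record whether it was reached.
- **Intention-to-treat rate:** the same events in all women injected with ICG, in line with Section 6. This should not be the main rate. Since "The ICG injection will be performed immediately before placement of surgical port and docking the robot", the injected set includes women converted before any SLN dissection, who would dilute a procedure-specific rate.
- **Supplement:** the current set with at least one SLN removed, labelled as such.

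In Appendix 2, widen the SLN complications field from removal to detection, dissection and removal, so that it matches Table 10.2.

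The cost is a short text edit and a small change to the form. Table 10.2 already captures dissection-phase events, but for women already operated on the start of detection may have to be taken from the operative record. The reported rate may be slightly less favourable.

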5.0 TREATMENT PLAN/ FOLLOW UP

Patients with metastatic SLN's shall be planned for a restaging procedure including pelvic and paraaortic lymph nodes.

Importantly, all intraoperative adverse events associated with the study intervention and the study drug (ICG) will be recorded in protocol as the separate time used for the detection and removal on SLN's. Likewise, complications associated with the restaging procedure shall be included on an intention to treat basis.(additional CRF)

All adverse events, including postoperative until 30 days, shall be evaluated whether attributable to the study intervention or not.

Measurement of leg volume as an objective parameter of lymphedema shall be performed at one and two year follow up and at symptoms.

Symptoms associated with lymphedema shall be evaluated by a designated QoL Form used before surgery, after surgery at symptoms, and at one and two years after surgery. A symptoms score shall be used at every follow up.

NOTE: Surgeons' skill and adherence to protocol will be verified as described above.

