11. STATISTICAL CONSIDERATIONS

This study is designed to evaluate the ability of the sentinel node (SLN) technique to determine pelvic lymph node metastases in patients with low- and high risk endometrial cancer as a replacement for a full lymphadenectomy in the latter and as an increased diagnostic procedure in the former.

The main statistical endpoint will be to evaluate the SLN concept by a non-inferiority analysis, i.e its ability to detect nodal metastatic disease compared with an estimated proportion which with a 50/50% distribution of LREC and HREC result in approximately 12% of women having pelvic nodal metastases. This will be tested against 8% metastatic SLN's as null-hypothesis. With a one-sided analysis (Alfa-error of 5% and 80% power) 362 patients need to be included with a planned interim analysis after 150 patients.

If then 22 or more patients are identified as SLN-node positive the null-hypothesis will be rejected and the study closed. If 12 or fewer patients are identified as SLN node positive the study will be closed for futility. If the number of node positive patients is between 12 and 21 the study will continue to enroll a total of 362 patients (Fleming, 1982).

The measurements of leg volume/lymphedema are based on an estimated risk for lymphedema following SLN only of 1% (null hypothesis) compared with the group of SLN positive (HREC and LREC) with an estimated risk of 4% (20% node positive with 20% risk of lymphedema) with an estimated distribution between group of 88% SLN negative and 12% SLN positive with restaging (SLN+LND). A total of 169 patients need to be included with a planned interim analysis after 65 patients. If 3 or more patients in the SLN+LND group have lymphedema the null hypothesis can be rejected provided no more than one patient in the SLN only group have developed lymphedema.

BIBLIOGRAPHY

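### The only planned lymphedema test is a count rule with very low power; an exact two-group test on the 10% cut, with a supportive analysis of measured leg volume, would use the same data better

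*Combined protocol and SAP*

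**What the plan says.** Section 5.0 sets the postoperative schedule: "Measurement of leg volume as an objective parameter of lymphedema shall be performed at one and two year follow up and at symptoms". The table in Section 7.0 marks "Measurement of leg volume" both preoperatively and postoperatively, so each woman has her own baseline.

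Section 8.0 defines the outcome by a cut: "An increase in leg volume of 10 % or more compared with the preoperative volume will be defined as a new onset of lymphedema".

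Section 11 contains the only lymphedema inference. It takes a 1% risk after SLN only as the null value. The SLN-positive group is entered "with an estimated risk of 4% (20% node positive with 20% risk of lymphedema" (the bracket closes there). The groups are expected to split 88% to 12%. The size is "A total of 169 patients need to be included with a planned interim analysis after 65 patients". The decision rule reads "If 3 or more patients in the SLN+LND group have lymphedema the null hypothesis can be rejected provided no more than one patient" in the SLN-only group is affected.

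No analysis of volume as a continuous measure is planned, and no standard deviation or distribution of volume change is given.

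**The concern.** Two separate steps can lose power. The first is the cut: with about 20 women in the SLN+LND group and a risk of 4%, only 20 × 0.04 = 0.8 events are expected, and changes under 10% do not enter the test. The second is the count rule. It is stricter than a standard two-group test, and one of its two conditions depends only on the SLN-only group.

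If the rule is applied as written, the most likely result is a failure to reject, even if restaging does raise the risk. That could be reported as no difference in lymphedema although the trial had little chance of showing one. The volumes needed for a better analysis are already being collected.

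**Working it through.** **Inputs.** From Section 11: N = 169, interim at 65, split 88/12, risk 1% after SLN only, and 4% or 20% for the other group (both figures appear in the same sentence). Group sizes: 0.12 × 169 = 20.3, so 20; the remaining 149 are SLN only. Assumptions: one-sided 5% (stated for the main endpoint only) and every woman measured.

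**1. The plan's own 169.** It reproduces as a one-sample, two-stage binomial design on all patients, with X1 ~ Bin(65, p) and X2 ~ Bin(104, p). Reject if X1 ≥ 3; stop for futility if X1 = 0; otherwise reject if X1 + X2 ≥ 5.

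P(reject) = P(X1 ≥ 3) + Σ P(X1 = x) · P(X2 ≥ 5 − x), for x = 1, 2.

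This is 0.0443 at p = 0.01 and 0.8003 at p = 0.04, and 169 is the smallest N that works with these bounds. Only the 3 is written in the plan; the 0 and the 5 are inferred. So 169 was not sized for comparing two groups of 149 and 20.

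**2. The written count rule at 149 versus 20.** Power = P(Bin(20, p1) ≥ 3) × P(Bin(149, 0.01) ≤ 1).

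- SLN-only condition: 0.99^149 + 149 × 0.01 × 0.99^148 = 0.224 + 0.337 = 0.560. It fails 44% of the time at the assumed 1%.
- p1 = 4%: 0.0439 × 0.560 = 0.025.
- p1 = 20%: 0.794 × 0.560 = 0.445.
- If the rule is meant for the interim (57 versus 8), power is 0.3% and 18%.

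**3. Fisher exact test on the same cut.** Full enumeration, one-sided 5%: 12.5% at 1% versus 4%, and 86.7% at 1% versus 20%.

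**4. Measured scale, common normal shift (assumption).** The two tail rates fix the standardised difference whatever the SD: d = z(0.99) − z(1 − p1).

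- 4%: d = 2.326 − 1.751 = 0.576. Noncentrality = 0.576 × √(149 × 20 / 169) = 2.42; t-test power 77.7%.
- 20%: d = 2.326 − 0.842 = 1.485; power above 99.9%.

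**5. Measured scale, other shapes (simulated, assumptions).**

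| Shape | 1% vs 4% | 1% vs 20% |
|---|---|---|
| Skewed, graded effect (noise SD 3–4 points) | 26–43% | 93–99% |
| All-or-none, pooled t (noise SD 2–4, swelling 15–20 points) | 14–24% | 71–91% |
| All-or-none, Welch t (same data) | 4–8% | 47–62% |
| All-or-none, Fisher on the cut (same data) | 9–12% | 72–86% |

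**6. Actual type I error when both risks are 1%.** Count rule 0.001004 × 0.560 = 0.06%; Fisher 1.0%; pooled t about 5%. Part of the power gap is therefore alpha that the discrete tests leave unused.

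**The case against.** A reader might infer that the 10% cut discards most of the information. Under a common normal shift that is right: a cut exceeded by 1–4% of women keeps about 7–19% of it. But the plan gives no distribution, and if a few women swell markedly while the rest do not, step 5 shows the advantage over Fisher shrinking or reversing. Against the count rule the gain can be as small as about 2 points (Welch 4.5% versus 2.5% at noise SD 2 and swelling of 20 points). The documents do not support the unconditional claim.

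A reader might also infer that the choice of scale is the problem whatever the risk after SLN+LND. At 20% it is not: Fisher on the same cut reaches 87%, so much of the shortfall to 44.5% comes from the count rule.

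A third tempting step is to replace the risk comparison by a model of mean volume. That changes the question, because Section 11 concerns the risk of lymphedema. The groups are not randomised, and Section 2 says nodal status determines adjuvant treatment. Weight appears on the baseline and surgical forms but not on the follow-up forms supplied, so weight change could not be adjusted for. Averaging both legs would also dilute one-sided swelling: in simulation (noise SD 3, swelling 12–15 points, between-leg correlation 0.5, all assumed) power at 20% fell to 46–70%, below Fisher.

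All these objections stand. They limit the claim and the remedy, but they do not defend the count rule or the absence of any volume analysis. The LYMQOL questionnaire and the symptom score do capture milder effects, but no analysis of them is stated either.

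**Conclusion.** The point holds in a limited form. The count rule is a poor test of the plan's own hypothesis: 2.5% power at 1% versus 4% and 44.5% at 1% versus 20%, with a 44% chance of failing on the SLN-only condition alone. An ordinary exact test on the same definition has 12.5% and 87%. These figures rest on 149 versus 20 women with complete follow-up; the Fisher figures also assume a one-sided 5% level.

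The further gain from using measured volume is conditional. It is large if swelling is a general or graded shift (78% at 1% versus 4% under the normal model) and small, absent or negative against Fisher if swelling is all-or-none. The calculations used unadjusted t tests, so they do not give the power of a baseline-adjusted model. They support adding a volume analysis, but not making it the sole test. This is an inexpensive improvement to the analysis and does not show that the 10% definition is wrong.

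Separately, the 4% is 20% × 20%, a product of two rates rather than the risk among women who had SLN+LND. The 20% node-positive figure also disagrees with the 12% in the same sentence. These must be reconciled whichever test is used.

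**What to change.** In Section 11:

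- Keep the 10% increase as the clinical definition. Replace the count rule with an exact two-group test of the lymphedema rates, at a stated level and sidedness, with exact confidence intervals for each group's rate and an interval for the difference.
- Add, as a pre-specified supportive analysis, an ANCOVA of log postoperative on log preoperative leg volume. Use one year as the main time point (the overview plan and Section 5.0 both include it) and two years as the second. Analyse by leg, allowing for the pairing within a woman, or use a defined worse-leg summary, so that one-sided swelling is not diluted. Report the SLN+LND to SLN-only ratio with its confidence interval.
- State that the comparison is non-randomised and open to weight change and adjuvant treatment.

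The cost is revised wording and one extra model, with no new patients or measurements. The downside is that a mean volume ratio is less direct clinically than an event rate, which is why the 10% rate remains the main comparison.
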